Unique study approval ID (Sweden): 2019-05490

Official title: Improving care for children with congenital heart disease by cardiovascular biomarker profiling and advanced non-invasive cardiac imaging techniques.

Statistical analysis plan (date): 25th of Oct. 2020

Study protocol summary:

Study type & outcome measure for cases:

- Case-control study to evaluate diagnostic usefulness of non-invasive cardiac imaging measures and cardiovascular biomarkers in children.
- Need for open heart surgery or cardiac catheter intervention to treat predefined congenital heart disease lesions leading to pulmonary over-circulation (as below).

Enrolment:

After local advertisement and written informed consent (dedicated healthcare regions in Sweden).

Controls (0-17 years) without history or presence of cardiovascular disease at enrolment:

Number of assessments: 1 (at enrolment)

Type of assessments in local paediatric cardiology ambulatory / out-patient clinic settings:

1. Clinical evaluation cardiovascular examination by paediatric cardiologist
2. Standard 12 lead ECG recording
3. Transthoracic echocardiography examination (predefined standard paediatric protocol including but not limited to 2D, Doppler, TDI)
4. Cardiac magnetic resonance (CMR) evaluation of the heart using predefined sequence protocol (including 4D flow assessments) for comparison to cases reaching outcomes (matched subgroup)
5. Peripheral blood sampling for cardiovascular biomarker batch analysis (O-link proximity extension assay of 96 markers and quantitative analysis of selected biomarkers, e.g. NT-pro-BNP)
6. Optional saliva sampling at enrolment and/or retrieval of dried blood samples from neonatal screening laboratory if available for batch analysis and comparison to standard blood sample cardiovascular biomarkers (O-link proximity extension assay of 96 markers and quantitative analysis of selected biomarkers, e.g. NT-pro-BNP)

Cases (0-17 years) without treated congenital heart disease by open heart surgery or cardiac catheter intervention at enrolment:

Included lesions of congenital heart disease leading to pulmonary over-circulation:

- Atrial septal defect (ASD)
- Ventricular septal defect (VSD)
- Patent ductus arteriosus (PDA)
- Partial anomalous pulmonary venous drainage (PAPVD)
- Aorto-pulmonary window (APW)

Number of assessments:

- Minimum 2 (at enrolment and 6-12 months after outcome is reached)

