Unique study approval ID (Sweden): 2019-05490

Official title: Improving care for children with congenital heart disease by cardiovascular biomarker profiling and advanced non-invasive cardiac imaging techniques.

Statistical analysis plan (date): 25th of Oct. 2020

Aims:

Diagnostic test evaluations of the cardiovascular system in paediatric controls and cases of defined congenital heart disease lesions, in line with e.g. STARD guidelines, to improve the early prediction of the studied outcome (need for open heart surgery or cardiac catheter intervention in cases).

Diagnostic methods:

1. Echocardiography evaluation:

- selected echocardiographic measure (test individual measures) will be selected to predict outcome (need for open heart surgery or cardiac catheter intervention)

- selected echocardiographic measures (test group of measures) will be selected to predict outcome (as above)

2. Cardiac magnetic resonance (CMR) evaluation:

- selected CMR measure (test individual measures) will be selected to predict outcome (as above)

- selected CMR measures (test group of measures) will be selected to predict outcome (as above)

3. Cardiovascular biomarkers:

- selected cardiovascular biomarker (test individual markers) will be selected to predict outcome (as above)

- selected cardiovascular biomarkers (test groups of markers) will be selected to predict outcome (as above)

Data collection:

- estimation of sample size based on previous studies (power 0.8, alpha 0.05)

- clinical data collection according to predefined criteria (anonymised electronic database)

- electronic storage of echocardiography / cardiac magnetic resonance imaging for analysis

- storage of cardiovascular biomarker samples under standardised conditions until batch analysis

- anonymised data analysis using established statistical methods

Data analysis:

- descriptive statistics / frequency tables of all enrolled subjects (n, %, mean/SD, median/IQR).

- parametric / non-parametric tests to compare controls and cases and changes in cases over follow-up period of study

- logistic regression modelling to identify risk factors / create models that are suitable to predict outcome in cases (need for open heart surgery or cardiac catheter intervention)

- receiver operating characteristics curves (ROC) / area under the curve (AUC) analysis for proposed new diagnostic tests that may help to predict outcome in cases (see above)

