- propose risk factor scoring system to predict outcome in cases (see above)

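### The SAP builds a risk score by selecting markers and fitting logistic regression with no shrinkage, internal validation or calibration; if selection is data-driven and cases are few, risks would probably be too extreme, and AUC cannot show it

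*SAP*

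**What the plan says.** Under Diagnostic methods, the SAP lists echocardiography, CMR and biomarkers separately. For each it plans to pick measures, singly and in groups, for their ability to predict intervention. The biomarker line reads: "selected cardiovascular biomarkers (test groups of markers) will be selected to predict outcome (as above". The protocol (controls, type of assessments, item 5) gives the panel as "O-link proximity extension assay of 96 markers and quantitative analysis of selected biomarkers, e.g. NT-pro-BNP".

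Under Data analysis, the SAP then plans three steps:
- "logistic regression modelling to identify risk factors / create models that are suitable to predict outcome in cases";
- ROC curves and "area under the curve (AUC) analysis for proposed new diagnostic tests";
- "propose risk factor scoring system to predict outcome in cases".

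The only general statement on method is "anonymised data analysis using established statistical methods" (Data collection). The same section gives power 0.8 and alpha 0.05, without a resulting sample size.

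Neither document states the number of cases, the expected number of interventions, the number of predictors, a selection rule, any penalisation or shrinkage, any internal or external validation, or any measure of calibration. The AUC line is attached to the proposed tests, so the scoring system has no performance measure of its own.

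**The concern.** When predictors are chosen because they look predictive in the same children, and their coefficients are then estimated in those children, the coefficients tend to be too large. The more candidates per event, the worse this is. In new children, high predicted risks are then too high and low ones too low.

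AUC uses only the order of the predictions, so every stated risk can be wrong while the AUC stays the same. The plan names no other measure. A score meant to predict which children will need surgery or catheter intervention could therefore be published with overstated weights and an optimistic AUC, and no planned output would warn of it.

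**Working it through.** The plan gives no sample size, event count or AUC, so there is no figure to reproduce. The only numerical inputs from the documents are the 96 markers, power 0.8 and alpha 0.05. Everything else below is assumed.

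**1. A plausible scale for the number of cases.** If the sample size came from comparing two means (the SAP does not say so), with a two-sided alpha, n per group = 2(1.960 + 0.842)²/d². This gives 175, 63 or 25 per group for standardised differences d of 0.3, 0.5 or 0.8. Low hundreds of cases or fewer is therefore a reasonable assumption, but no more than that.

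**2. AUC cannot see the fault.** AUC depends on the ranks of the linear predictor. In the simulations below, multiplying it by 0.4 left the median AUC unchanged in all four settings (0.78, 0.84, 0.80, 0.77).

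**3. Calibration on the development data cannot see it either.** Maximum likelihood solves Σxⱼ(y − p) = 0 for every predictor and the intercept. Hence Σ(y − p) = 0 and Σ LP(y − p) = 0, where LP is the linear predictor. These are the calibration equations with intercept 0 and slope 1. The simulated apparent slope was 1.00 throughout.

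**4. Size of the over-extremeness.** The calibration slope is b in logit P(Y = 1) = a + b·LP, fitted in new children. Values below 1 mean risks that are too extreme. Assumed inputs: 106 candidates (96 markers plus 10 echo measures), pairwise correlation 0.3, 6 true predictors with log-OR 0.15 or 0.3 per SD, event fraction about 0.3 or 0.5, unpenalised fits, 60 replicates per setting and 20,000 new subjects. Ranges of median slopes:

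| Cases | Top 5 or 10 by univariable test | Forward selection, p<0.05 | 3 or 6 pre-specified |
|---|---|---|---|
| 100 | 0.33–0.50 | 0.04–0.13 | 0.47–0.82 |
| 200 | 0.43–0.65 | 0.16–0.43 | 0.62–0.93 |
| 400 | 0.58–0.77 | 0.34–0.58 | 0.82–1.01 |
| 1000 | 0.74–0.91 | 0.55–0.81 | 0.91–0.98 |

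Further runs of data-driven selection under other assumed inputs gave 0.25–0.50 at 100 cases, 0.53–0.71 at 200 and 0.83–0.84 at 400. Taken together, the data-driven ranges are about 0.04–0.5, 0.16–0.7 and 0.34–0.84.

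To read a slope of 0.5 with calibration intercept 0: a stated risk of 80% has logit ln(0.8/0.2) = 1.386. Half of that is 0.693, which is a risk of 67%. Likewise, a stated 20% becomes 33%.

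**5. Closed-form check.** For expected shrinkage S = 0.9 with P candidate parameters, n = P/((S − 1) ln(1 − R²cs/S)). Here R²cs is Nagelkerke R² times its maximum, 1 − (φ^φ(1 − φ)^(1−φ))², and φ is the event fraction.
- P = 106, φ = 0.5, Nagelkerke R² 0.5: R²cs = 0.5 × 0.75 = 0.375. ln(1 − 0.375/0.9) = −0.539, so n = 106/0.0539, about 1,970.
- P = 106, φ = 0.3, Nagelkerke R² 0.15: R²cs = 0.15 × 0.7053 = 0.1058. ln(1 − 0.1058/0.9) = −0.1250, so n is about 8,480.
- n is proportional to P. With the 96 panel markers alone the range is about 1,780 to 7,680; with 5 candidates it is 93 to 400.

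**6. Would the remedy show and reduce the problem?** Top-5 models with about 30% events, 40 replicates, and a bootstrap that repeats the selection:

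| log-OR, cases | Apparent / corrected / true AUC | Apparent / bootstrap / true slope | Ridge slope |
|---|---|---|---|
| 0.15, 100 | 0.78 / 0.66 / 0.60 | 1.00 / 0.55 / 0.32 | 1.20 |
| 0.3, 100 | 0.84 / 0.76 / 0.71 | 1.00 / 0.61 / 0.48 | 1.14 |
| 0.3, 200 | 0.80 / 0.74 / 0.71 | 1.00 / 0.72 / 0.61 | 1.05 |
| 0.3, 400 | 0.77 / 0.73 / 0.72 | 1.00 / 0.79 / 0.78 | 1.14 |

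Resampling reveals the problem but understates it at 100 cases. Penalisation removes most of it in the median, but one study is one draw. In one setting with 100 cases, the 10th–90th percentile range of the ridge slope was 0.44 to 8.2.

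**The case against.** A reader might infer four stronger things, none of which the documents support.

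- *The SAP commits to unpenalised regression.* It leaves the estimation method open, and a penalised fit would satisfy its wording.
- *All 96 markers and the echo measures enter one model.* The modalities are listed separately, each with selected measures, and pooling is never mentioned. The argument does not need it, because the panel alone supplies 96 candidates.
- *The risks will certainly be far too extreme.* That depends on cases, events, predictors and selection rule, none of which is stated. Three or six pre-specified predictors at 400 cases gave slopes of 0.82–1.01.
- *Candidates must equal or outnumber events.* With no event count in the documents, this cannot be known.

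A further objection is fair. The SAP proposes a scoring system and does not promise percentage risks. A score used only to rank children, or with a cut-off, depends mainly on discrimination. That narrows the harm but does not remove it: apparent AUC was also optimistic (0.84 against a true 0.71 at 100 cases), and the plan has no step to correct it.

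It is also right that ridge for every model would be a matter of preference. Ridge keeps all the markers, which sits badly with a score built on selected ones, and its slope is unstable at small samples.

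**Conclusion.** The concern holds conditionally. What the documents establish is that a score is to be built from selected measures by logistic regression, with no stated shrinkage, internal validation or calibration, and with a rank-based measure as the only check. That AUC and apparent calibration are blind to over-extreme risks needs no assumption beyond a maximum-likelihood fit for the latter.

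The size is conditional on data-driven selection and on cases in the low hundreds or fewer. Under those assumptions, over-extreme weights are probable and can be severe, with the slopes given above. With a short pre-specified list and 400 or more cases, the problem is small. The plan fixes neither condition, so nothing in it protects against the bad end of the range. It should be changed before the analysis; it does not undermine the data collection.

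**What to change.** Add to the SAP, for any model or score whose predictors are chosen using the data:

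1. Bootstrap or cross-validate the whole procedure, repeating the marker selection within every resample.
2. Report optimism-corrected calibration slope and intercept and Brier score beside optimism-corrected AUC, for the scoring system as well as for the individual tests.
3. Derive score points from shrunken coefficients. Where a score on selected markers is wanted, use a penalised fit such as the lasso or elastic net. Otherwise, multiply the coefficients by the resampled slope and re-estimate the intercept.
4. Report the shrinkage estimate with its uncertainty.

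Cost: SAP wording and a little more analysis, with no new data or visits. Reported performance will look less favourable, and penalised coefficients do not carry conventional p-values. At about 100 cases the shrinkage estimate is imprecise and the bootstrap slope still understates the problem, so a score from a sample of that size should be presented with that caveat.
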